### 8.3.2 DEFINITION OF SERIOUS ADVERSE EVENTS (SAE)

An adverse event (AE) or suspected adverse reaction is considered "serious" if, in the view of either the investigator or sponsor, it results in any of the following outcomes: death, a life-threatening adverse event, inpatient hospitalization or prolongation of existing hospitalization, or a persistent or significant incapacity or substantial disruption of the ability to conduct normal life functions.

Serious adverse events (SAEs) will be defined as:

- Death, believed to be related to the study procedures, or a death that is unexpected considering the acuity of a subject.
- A life-threatening experience, including severe infusion reactions, believed to be related to the study procedures.
- Persistent or significant disability or incapacity that is of greater frequency or severity than what would be normally expected in the course of critical illness.
- An event that jeopardizes the human subject and may require medical or surgical treatment to prevent one of the preceding outcomes and is not expected in the subject's ICU course.

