#### 8.3.6 SERIOUS ADVERSE EVENT REPORTING

The study clinician will immediately report to the IRB any serious adverse event, whether or not considered study intervention related, including those listed in the protocol or investigator brochure and must include an assessment of whether there is a reasonable possibility that the study intervention caused the event. Study endpoints that are serious adverse events (e.g., all-cause mortality) must be reported in accordance with the protocol unless there is evidence suggesting a causal relationship between the study intervention and the event (e.g., death from anaphylaxis). In that case, the investigator must immediately report the event to the sponsor. All serious adverse events (SAEs) will be followed until satisfactory resolution or until the site investigator deems the event to be chronic or the participant is stable.

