#### 9.4.4 SAFETY ANALYSES

All AEs and SAEs will be presented and compared between groups. Mortality and hospital readmission rates will also be presented and compared between groups.

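### Section 8.3.2 defines SAEs in two ways that do not match, and the operative list filters on unblinded relatedness or expectedness, so the between-arm SAE comparison in 9.4.4 is skewed

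*Combined protocol and SAP*

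**What the plan says.** All references are to the combined protocol and SAP.

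- **Section 8.3.2, opening paragraph.** An event is serious according to its outcome: death, threat to life, "inpatient hospitalization or prolongation of existing hospitalization", or lasting incapacity. Neither relatedness nor expectedness enters.
- **Section 8.3.2, operative list.** The same section then states what SAEs will be, in four items:
  - Fatal events have two routes in, attribution or surprise: "Death, believed to be related to the study procedures, or a death that is unexpected considering the acuity of a subject".
  - Threats to life have one route only, attribution: "A life-threatening experience, including severe infusion reactions, believed to be related to the study procedures".
  - Lasting harm needs no attribution but must exceed the usual course: "Persistent or significant disability or incapacity that is of greater frequency or severity than what would be normally expected in the course of critical illness".
  - Other jeopardizing events also need no attribution; the item ends with the condition "prevent one of the preceding outcomes and is not expected", judged against the usual ICU stay.
- **Section 8.3.6.** The study clinician reports "any serious adverse event, whether or not considered study intervention related".
- **Section 9.4.4.** "All AEs and SAEs will be presented and compared between groups". The section then turns to two further outcomes: "Mortality and hospital readmission rates will also be presented and compared between groups".
- **Section 8.3.1.** Adverse events are defined without regard to relatedness, but recording is confined to six conditions: infusion reactions, venous thromboembolism, myocardial infarction, non-hemorrhagic stroke, bloodstream infection, and hypertensive events in the hour after study drug.
- **Sections 6.3, 8.3.3.2 and 8.3.3.3.** Clinicians and participants know the allocation. The clinician who examines the patient grades relatedness, and the principal investigator decides expectedness.

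**The concern.** A between-arm comparison of harms is interpretable only if an event has the same chance of being counted in either arm. Here the rule for counting a life-threatening event includes a causal judgment, made by someone who knows the allocation, about procedures that are far more extensive in one arm. Control patients have research blood draws and follow-up assessments but no study drug. The relatedness grades in 8.3.3.2 are framed around timing after administration of the intervention, which a control patient never has.

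At stake is the reading of the SAE table. Section 2.3.1 says that existing trials do not rule out a clinically important increase in adverse events with EPO, quoting a relative risk for SAEs of 1.11 (95% CI 0.94 to 1.31). Section 9.4.9 says the exploratory results will inform a phase III trial. A modest signal of that kind can be created or hidden by the counting rule.

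**Working it through.** **Step 1. The plan's own figure.** The documents give no SAE rate, margin or power, so there is no figure to reproduce. The only design inputs needed are the enrolled total of 100 (Section 9.2) and 1:1 allocation (Section 6.3), giving about 50 per arm.

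**Step 2. The four operative criteria, side by side.**

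| Criterion in the 8.3.2 list | Filter | Can a control patient meet it? |
|---|---|---|
| Death | related, or unexpected for acuity | yes, through the second limb |
| Life-threatening event | related only | almost never |
| Disability | beyond what critical illness explains | yes |
| Other jeopardizing event | not expected in the ICU course | yes |

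One criterion is asymmetric by construction. The other three are open to both arms, but each contains an expectedness judgment that nothing in the documents masks to allocation. Blinded assessment is described only for the 1- and 3-month visits (Section 4.1).

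**Step 3. Consistency.** An unrelated life-threatening event is an SAE under the opening paragraph of 8.3.2 but not under the list. Section 8.3.6 asks for unrelated SAEs to be reported, yet under the list an unrelated life-threatening event is not an SAE at all. The list also omits hospitalization and its prolongation, which the opening paragraph includes. Section 9.4.4 does not choose between the two definitions.

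**Step 4. How large could the asymmetry be?** This illustrates the life-threatening criterion alone; every rate is an assumption. Let *p* be the true risk of such an event, equal in both arms, and let *a* and *c* be the shares attributed to study procedures in the intervention and control arms. The expected filtered counts are 50 × *p* × *a* and 50 × *p* × *c*; the true counts are 50 × *p* in each arm. For example, *p* = 0.10, *a* = 0.50, *c* = 0 gives 50 × 0.10 × 0.50 = 2.5 versus 0, against true counts of 5 and 5. Section 9.4.4 names no test, so a two-sided Fisher test at 0.05 is assumed. The last four columns give expected counts, with the chance of a false rejection in brackets.

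| *p* | True counts | *a*=10%, *c*=0 | *a*=25%, *c*=0 | *a*=50%, *c*=0 | *a*=50%, *c*=25% |
|---|---|---|---|---|---|
| 10% | 5 v 5 | 0.5 v 0 (0.0%) | 1.25 v 0 (0.2%) | 2.5 v 0 (3.8%) | 2.5 v 1.25 (1.2%) |
| 20% | 10 v 10 | 1.0 v 0 (0.1%) | 2.5 v 0 (3.8%) | 5.0 v 0 (38%) | 5.0 v 2.5 (6.3%) |
| 30% | 15 v 15 | 1.5 v 0 (0.4%) | 3.75 v 0 (17%) | 7.5 v 0 (78%) | 7.5 v 3.75 (12%) |

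Whenever *a* exceeds *c*, the expected count is tilted against the intervention arm. Both arms lose events, but control loses more. Whether a test would mislead depends on the assumed rates: in much of the grid false rejection stays below 5% and the harm is a distorted table. Counting by seriousness alone (the true-count column) keeps false rejection at or below 5%.

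**The case against.** The strongest reply is that the trial's safety comparison does not rest on the filtered list, and most of that stands. Venous thromboembolism, infarction, stroke and bloodstream infection are recorded in both arms regardless of cause, from consent to 3 months after hospitalization (Sections 8.3.1 and 8.3.4), and 9.4.4 compares them as AEs. All-cause mortality and readmission are compared separately, by log-rank and Gray's tests (Section 9.4.3). A reader might infer that a real excess of thrombosis or infarction would vanish from the comparison if judged expected. The documents do not support that: such an event could leave the SAE row but would stay in the AE comparison.

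A reader might also infer that control patients can hardly have an SAE of any kind. That fits one criterion of four. Unexpected death, excess disability and unexpected jeopardizing events carry no relatedness requirement, and for them the risk is uneven judgment, not exclusion.

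Two further replies carry some weight. Because the definitions conflict, the filtered rule is not certain to be the one tabulated; however, the list is worded as the operative definition, and leaving the choice open is itself a defect in 9.4.4. Safety oversight is deferred to a separate monitoring plan (Section 10.1.6), which may contain adjudication rules that cannot be checked here.

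Finally, the six-condition limit in 8.3.1 is deliberate, because many unrelated events are expected in this population. A remedy that required recording every serious event would undo that choice and is not proposed.

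**Conclusion.** The point holds in a limited form. Section 8.3.2 contains two SAE definitions that do not match, and the operative one conflicts with 8.3.6. If the plan is followed as written, the life-threatening part of the 9.4.4 SAE comparison is asymmetric by construction. The remaining parts are exposed to open-label judgment of expectedness, where the direction of any bias cannot be predicted.

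The size is unknown, because no SAE rates are given. The illustration ranges from negligible (0.5 versus 0 expected, essentially no false rejections) to serious (7.5 versus 0, 78% false rejection). It rests on assumed risks and attribution shares, equal true risk in the two arms, 50 patients per arm and an assumed Fisher test, and it covers one criterion, not the SAE total. It does not support a claim that the trial can give no unbiased safety signal. The unfiltered comparisons of AEs, mortality and readmission remain, and the hemoglobin endpoint is unaffected. The definition should be corrected before the safety tables are produced.

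**What to change.** 1. Reconcile 8.3.2 with 8.3.6, so that one definition of seriousness applies throughout. Keep the filtered list only as a trigger for expedited reporting, and label it as such.
2. In 9.4.4, name the definition used. For the between-arm comparison, count events in both arms by seriousness alone (the opening paragraph of 8.3.2), applied to the listed types both arms can have (venous thromboembolism, myocardial infarction, stroke, bloodstream infection), plus all-cause death.
3. Keep relatedness and expectedness as separate descriptive fields that do not decide whether an event enters the comparison.
4. Present infusion reactions and hypertensive events in the hour after dosing descriptively, for the intervention arm only, since control patients cannot have them as defined.

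The cost is wording changes and slightly more classification work on events already recorded. Section 8.2 already provides for daily record review and collects relationship to the intervention as its own item. The scope of AE recording, the sample size and the treatments do not change. Assigning seriousness still takes some judgment, but about an event's outcome and not its cause.

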### 8.3.3 CLASSIFICATION OF AN ADVERSE EVENT

#### 8.3.3.1 SEVERITY OF EVENT

For adverse events (AEs), the following guidelines will be used to describe severity.

- **Mild** – Events require minimal or no treatment and do not interfere with the participant's clinical course.
- **Moderate** – Events result in a low level of inconvenience or concern with the therapeutic measures. Moderate events may cause some interference with the subject's clinical course.
- **Severe** – Events interrupt a participant's clinical course and may require systemic drug therapy or other treatment. Severe events are usually potentially life-threatening or incapacitating.

#### 8.3.3.2 RELATIONSHIP TO STUDY INTERVENTION

All adverse events (AEs) must have their relationship to study intervention assessed by the clinician who examines and evaluates the participant based on temporal relationship and his/her clinical judgment. The degree of certainty about causality will be graded using the categories below. In a clinical trial, the study product must always be suspect.

- **Definitely Related** – There is clear evidence to suggest a causal relationship, and other possible contributing factors can be ruled out. The clinical event occurs in a plausible time relationship to study intervention administration and cannot be explained by concurrent disease or other drugs or chemicals. The response to withdrawal of the study intervention (dechallenge) should be clinically plausible. The event must be pharmacologically or phenomenologically definitive, with use of a satisfactory rechallenge procedure if necessary.
- **Probably Related** – There is evidence to suggest a causal relationship, and the influence of other factors is unlikely. The clinical event occurs within a reasonable time after administration of the study intervention, is unlikely to be attributed to concurrent disease or other drugs or chemicals, and follows a clinically reasonable response on withdrawal (dechallenge). Rechallenge information is not required to fulfill this definition.

- **Potentially Related** – There is some evidence to suggest a causal relationship (e.g., the event occurred within a reasonable time after administration of the trial medication). However, other factors may have contributed to the event (e.g., the participant’s clinical condition, other concomitant events). Although an AE may rate only as “possibly related” soon after discovery, it can be flagged as requiring more information and later be upgraded to “probably related” or “definitely related”, as appropriate.
- **Unlikely to be related** – A clinical event whose temporal relationship to study intervention administration makes a causal relationship improbable (e.g., the event did not occur within a reasonable time after administration of the study intervention) and in which other drugs or chemicals or underlying disease provides plausible explanations (e.g., the participant’s clinical condition, other concomitant treatments).
- **Not Related** – The AE is completely independent of study intervention administration, and/or evidence exists that the event is definitely related to another etiology. There must be an alternative, definitive etiology documented by the clinician.

#### 8.3.3.3 EXPECTEDNESS

The PI will be responsible for determining whether an adverse event (AE) is expected or unexpected. An AE will be considered unexpected if the nature, severity, or frequency of the event is not consistent with the risk information previously described for the study intervention.

#### 8.3.4 TIME PERIOD AND FREQUENCY FOR EVENT ASSESSMENT AND FOLLOW-UP

The occurrence of an adverse event (AE) or serious adverse event (SAE) may come to the attention of study personnel during study visits and interviews of a study participant presenting for medical care, or upon review by a study monitor.

As noted earlier, for this study we plan to observe for a specific set of AEs and this information will be captured on the appropriate case report form (CRF). Information to be collected includes event description, time of onset, clinician’s assessment of severity, relationship to study product (assessed only by those with the training and authority to make a diagnosis), and time of resolution/stabilization of the event. All AEs will be followed to adequate resolution.

Changes in the severity of an AE will be documented to allow an assessment of the duration of the event at each level of severity to be performed.

Study coordinators will record all listed reportable events with start dates occurring any time after informed consent is obtained through 3-months after hospitalization. At each study visit, the investigator will inquire about the occurrence of AE/SAEs since the last visit. Events will be followed for outcome information until resolution or stabilization.

#### 8.3.5 ADVERSE EVENT REPORTING

All adverse events will be indicated on the data forms for the study and on the specific adverse event report forms and all serious adverse events will be reported to the IRB within 24 hours of the research team learning about the event followed by a more detailed written report to the IRB. The following information about adverse events will be collected: 1) the onset and resolution of the event, 2) an assessment of the severity or intensity of the event, 3) an assessment of the relationship of the event to the intervention, and 4) any action taken because of event. The PI will report all potentially related SAEs to the NHLBI immediately after discovery (within 7 days).

#### 8.3.6 SERIOUS ADVERSE EVENT REPORTING

The study clinician will immediately report to the IRB any serious adverse event, whether or not considered study intervention related, including those listed in the protocol or investigator brochure and must include an assessment of whether there is a reasonable possibility that the study intervention caused the event. Study endpoints that are serious adverse events (e.g., all-cause mortality) must be reported in accordance with the protocol unless there is evidence suggesting a causal relationship between the study intervention and the event (e.g., death from anaphylaxis). In that case, the investigator must immediately report the event to the sponsor. All serious adverse events (SAEs) will be followed until satisfactory resolution or until the site investigator deems the event to be chronic or the participant is stable.

#### 8.3.7 REPORTING EVENTS TO PARTICIPANTS

Study coordinators will disclose any adverse events that are probably or definitively-related to the enrolled subject after review by the PI.

#### 8.3.8 EVENTS OF SPECIAL INTEREST

Not applicable

#### 8.3.9 REPORTING OF PREGNANCY

Not applicable

### 8.4 UNANTICIPATED PROBLEMS

#### 8.4.1 DEFINITION OF UNANTICIPATED PROBLEMS (UP)

The Office for Human Research Protections (OHRP) considers unanticipated problems involving risks to participants or others to include, in general, any incident, experience, or outcome that meets all the following criteria:

- Unexpected in terms of nature, severity, or frequency given (a) the research procedures that are described in the protocol-related documents, such as the Institutional Review Board (IRB)-approved research protocol and informed consent document; and (b) the characteristics of the participant population being studied;
- Related or possibly related to participation in the research (“possibly related” means there is a reasonable possibility that the incident, experience, or outcome may have been caused by the procedures involved in the research); and
- Suggests that the research places participants or others at a greater risk of harm (including physical, psychological, economic, or social harm) than was previously known or recognized.

#### 8.4.2 UNANTICIPATED PROBLEM REPORTING

The investigator will report unanticipated problems (UPs) to the reviewing Institutional Review Board (IRB) and to the principal investigator (PI). The UP report will include the following information:

- Protocol identifying information: protocol title and number, PI’s name, and the IRB project number;
- A detailed description of the event, incident, experience, or outcome;
- An explanation of the basis for determining that the event, incident, experience, or outcome represents an UP;
- A description of any changes to the protocol or other corrective actions that have been taken or are proposed in response to the UP.

To satisfy the requirement for prompt reporting, UPs will be reported using the following timeline:

- UPs that are serious adverse events (SAEs) will be reported to the IRB within 7-days of the investigator becoming aware of the event.
- Any other UP will be reported to the IRB and to the DCC/study sponsor within 10-days of the investigator becoming aware of the problem.
- All UPs should be reported to appropriate institutional officials (as required by an institution's written reporting procedures), the supporting agency head (or designee), and the Office for Human Research Protections (OHRP) within 10 days of the IRB's receipt of the report of the problem from the investigator.

#### 8.4.3 REPORTING UNANTICIPATED PROBLEMS TO PARTICIPANTS

Study coordinators will disclose UPs that are probably or definitively-related to the enrolled subject.

### 9 STATISTICAL CONSIDERATIONS

#### 9.1 STATISTICAL HYPOTHESES

In this study, we will perform a pilot pragmatic clinical trial testing a multi-faceted anemia intervention (optimized phlebotomy practice, decision support, targeted pharmacologic anemia treatment) to attenuate anemia development and promote functional recovery in the setting of critical illness

**Primary endpoint:** To assess the impact of the intervention on 1 month post-hospitalization hemoglobin concentrations.

**Secondary endpoint:** To assess the impact of the intervention on post-hospitalization functional outcomes and hemoglobin concentrations measured at 3 months.

Hypotheses: A multifaceted anemia intervention will increase hemoglobin concentrations and will improve functional recovery through 3 months after hospitalization.

#### 9.2 SAMPLE SIZE DETERMINATION

Power/sample size are calculated to detect a difference in the primary endpoint of hemoglobin at 1 month follow-up. Preliminary data show mean (standard deviation) hemoglobin levels of 10.8 (1.5) g/dL at 1 month among 636 subjects with similar inclusion/exclusion criteria receiving standard care. A total sample size of 74 (37 per group) provides 80% power to detect 1.0 g/dL improvement using a two-sample unequal variances t-test with 2-sided alpha of 0.05 to compare 1 month hemoglobin between randomized arms. Actual power is expected to be higher under the analysis approach, adjusting for pre-randomization prognostic variables to reduce residual variation. If adjustment variables account for 25% of the variation in 1 month hemoglobin ( $R^2$  for relationship between pre-randomization adjustment variables and outcome = 0.25), the sample size of 37 per group provides 90% power to detect a 1.0 g/dL improvement using analysis of covariance with 2-sided alpha of 0.05. While the analysis uses a linear mixed-effects model (LMM), power is not appreciably different for the LMM as compared to the unequal variances t-test or ANCOVA described here. Given expected dropout of up to 25% (death, loss to follow-up) resulting in loss of information, 100 subjects will be enrolled.

The study has not been powered for exploratory outcomes such as RBC transfusion, mortality, and readmissions, but this data will serve for hypothesis-generation for future, larger clinical trials.

#### 9.3 POPULATIONS FOR ANALYSES

As the primary approach, subjects will be analyzed using an intention-to-treat (ITT) approach. Secondarily, analysis will be performed using modified intention-to-treat.

